1.0 SYNOPSIS

1.1 Study Title

A three-arm, parallel group, multicentre, double-blind, randomized controlled trial evaluating the impact of GeneSight Psychotropic (GEN) and Enhanced-GeneSight Psychotropic (E-GEN), on response to psychotropic treatment in outpatients suffering from a major depressive disorder (MDD) and having had – within the current episode - an inadequate response to at least one psychotropic medication included in GEN.

1.2 Objectives

The first primary objective of this study is to compare the efficacy of GEN to treatment as usual (TAU) in improving response to psychotropic treatment in outpatients suffering from a major depressive disorder (MDD) and having had – within the current episode - an inadequate response to at least one psychotropic medication included in GEN.

The second primary objective for this study is to validate the clinical utility of the new Centre for Addiction and Mental Health (CAMH) markers and demonstrate the superior predictive capabilities of E-GEN as compared to GEN.

1.3 Interventions and Duration

Patient DNA will be collected for all participants and measured for variations in drug target genes and in drug metabolizing genes. Subsequently, recommendations for optimal choices and dose adjustments for the 33 most commonly prescribed antidepressant and antipsychotic medications will be provided to participants randomized to the GEN arm. This pharmacogenomics-based interpretive report will be provided to treating clinicians of patients in the GEN arm of the study, allowing clinicians to use the report to support their treatment decisions.

The E-GEN test incorporates into the existing GEN product new markers patented by CAMH and licensed by Assurex that are predictive of side effect of antipsychotic-induced weight gain (AIWG). The pharmacogenomics-based interpretive report from E-GEN will also be provided to treating clinicians of patients in the E-GEN arm of the study, allowing clinicians to use the report to support their treatment decisions.

Participants randomized to the TAU arm will also require collection of patient DNA. A pharmacogenomics-based interpretive report will again be generated from GEN, however, this report is not provided to the treating clinician until up to 28 days prior to the completion at 12 months of the study at which point the report will be provided to the participant. Therefore, patients in this arm will receive clinical treatment as usual, without the use or knowledge of pharmacogenetics results by their treating clinicians.

Research evaluation visits for all three arms will be completed at baseline, 4, 8 and 12 weeks. To capture long-term information, including comparison between GEN and E-GEN, and each test with TAU, follow-up will also be conducted at 6, 9, and 12 months. The information collected at months 6 and 9 will be by telephone interviews while participants will return for a physician visit at month 12.

1.4 Design and Outcomes

A multicentre, double-blind, randomized controlled trial examining three different treatment pathways. Participants will be stratified by outpatient treatment site. The primary outcome measure will be change in HAM-D₁₇ score between baseline and 8 weeks. Secondary outcomes will be measured by the 16-item Self-Report Quick Inventory of Depressive Symptomatology (QIDS-SR₁₆), 9-item Patient Health Questionnaire (PHQ-9), Generalized Anxiety Disorder 7-Item (GAD-7) Scale, Clinical Global Impression of Severity (CGI-S), Clinical Global Impression of Improvement (CGI-I), Clinical Global Impression Efficacy Index (CGI-EI), changes to initial prescribing based on availability of pharmacogenomic data, response rates to psychotropic medication, remission rates, time to response/remission, Udvalg for Kliniske Undersogelser (UKU) side effect rating scale, Frequency, Intensity, and Burden of Side Effects Ratings (FIBSER), weight gain, EuroQol (EQ-5D) and Short Form (36) health survey (SF-36) for quality of life, Pharmacogenetics in Psychiatry Follow-Up Questionnaire (PIP-FQ) for physician's attitude and experience to pharmacogenomic testing, healthcare resource utilization and productivity losses, healthcare costs and cost-effectiveness of GEN, E-GEN and TAU. Evaluation of early and long-term effects on primary and secondary outcomes will be completed.

1.5 Sample Size and Population

This study will enroll 570 participants who present with moderate to severe MDD as measured by a total score of ≥ 11 on the QIDS-C₁₆ and 16-item Self Report Quick Inventory of Depressive Symptomatology (QIDS-SR₁₆), and an inadequate response within the current episode to at least one psychotropic treatment included in the GEN.

2.0 ADMINISTRATIVE INFORMATION

2.1 Title

A three-arm, parallel group, multicentre, double-blind, randomized controlled trial evaluating the impact of GeneSight Psychotropic and Enhanced-GeneSight Psychotropic, on response to psychotropic treatment in outpatients suffering from a major depressive disorder (MDD) and having had – within the current episode - an inadequate response to at least one psychotropic medication included in GeneSight Psychotropic.

2.2 Trial Registration

ClinicalTrials.gov Identifier: NCT02466477

WHO Trial Registration Data Set:

<http://apps.who.int/trialsearch/Trial2.aspx?TrialID=NCT02466477>

2.3 Protocol Version

Issue date: 2 May 2017 Version: 1.5

2.4 Organizational Structure

2.4.1 MaRS EXCITE

This evaluation is being facilitated through the MaRS Excellence in Clinical Innovation and Technology Evaluation (“EXCITE”) program. The EXCITE program connects health technology innovators with experienced, award-winning researchers to get the right evidence and data needed to show the value of the technology and to facilitate discussions with relevant health system stakeholders to determine what it takes to get the technology adopted successfully. The goal of the program is to support the evaluation of new health technologies to develop a robust evidence package that can be used for both regulatory or licensing approval and reimbursement reviews and to connect the innovators with the health system concerning conditions needed for successful adoption of the technology.

2.4.2 Methodology Centre

Methodology Centres are responsible for overseeing the design and execution of EXCITE studies.

Topstone Research is a specialty contract research organization located in Toronto, Ontario Canada selected at the Methodology Centre for this study. Topstone provides supportive research infrastructure for academic institutions and primary care physicians.

The Programs for Assessment of Technology in Health (PATH), based at St. Joseph's Healthcare Hamilton, will be responsible for the economic evaluation associated with the study, as a part of the MaRS EXCITE program.

2.4.3 Trial Monitoring Committee

The Trial Monitoring Committee membership will be comprised of 5 experts (clinicians, scientists, and statisticians) that have relevant expertise and experience in clinical trials, statistics and treatment of MDD but are completely independent of the conduct of the trial, the PIs, the Trial Sponsor and/or the Trial Funders. The PIs may be asked to attend open sessions of the Trial Monitoring Committee meeting.

The Trial Monitoring Committee is the only group involved in the trial that will have access to unblinded data and its role is to review accumulating trial data (focusing on ethical, safety and efficacy endpoints), quality of trial conduct, trial progress, and compliance. It is also responsible for taking into consideration data emerging from other related studies, and in turn making appropriate recommendations. The Trial Monitoring Committee will agree on a Charter of Operations and the frequency of meetings as appropriate.

3.0 BACKGROUND AND RATIONALE

3.1 Major Depressive Disorder (MDD)

Major depressive disorder (MDD) is a highly prevalent(1) mental disorder and a leading source of disease burden worldwide(2). Epidemiological studies estimate 12-month and lifetime prevalence of MDD in Canada to be 4% and 10.8% respectively(3). MDD is expected to be the second greatest cause of disability by 2020 and has been shown to cause significant morbidity, affecting people's ability to work, function in relationships, and engage in social activities. Moreover, MDD increases the risk of suicidal ideation, attempted suicide, and death by completed suicide.

Prospective longitudinal studies of patient samples show that MDD is a chronic illness, characterized by remitting and recurrent depressive episodes (4, 5). A major depressive episode is characterized by a low mood or an inability to experience pleasure

(anhedonia), or both, for more than 2 weeks, combined with several cognitive and vegetative symptoms and the occurrence of distress or impairment(6).

Drugs currently available to treat depression can mostly be categorized having their main effect of increasing synaptic levels of the monoaminergic neurotransmitters. These include drugs that elevate norepinephrine (NE) (the tricyclic or tetracyclic antidepressants [TCAs]), those that increase serotonin (5-HT) (the selective serotonin reuptake inhibitors [SSRIs]), and those that increase both NE and 5-HT (the monoamine oxidase inhibitors [MAOIs]), and the norepinephrine and serotonin reuptake inhibitors [SNRIs](7, 8). While all antidepressants achieve similar levels of efficacy, treatment failures are relatively high ranging from 30 to 60%(9). Additionally, many of these compounds are associated with significant adverse events (AEs).

3.2 GeneSight Psychotropic (GEN)

The GeneSight Psychotropic (GEN) product is a pharmacogenomic decision support tool that helps clinicians to make informed, evidence-based decisions about proper drug selection. More specifically, patients are tested for clinically important genetic variants of multiple pharmacokinetic and pharmacodynamic genes that affect a patient's ability to metabolize, tolerate or respond to medications.

GEN individualizes psychotherapeutic selection and improves response to psychotropic medications by measuring nucleotide variations in eight genes: CYP1A2, CYP3A4, CYP2B6, CYP2C9, CYP2C19, CYP2D6; SLC6A4, and HTR2A. Results are analyzed using proprietary algorithms to recommend the selection and dosing of the 33 most commonly prescribed Health Canada approved antidepressant and antipsychotic medications (see Appendix I) including a full representation of the SSRI and SNRI drug classes. Tricyclic antidepressants, an MAOI, and typical and atypical antipsychotics are also represented. The test generates a report for each patient that stratifies antidepressant and antipsychotic medications into one of three "bins": "Green bin" medications – use as directed, "Yellow bin" medications – use with caution, and "Red bin" medications – use with increased caution and more frequent monitoring. Clinicians receive the easy to implement report within three days of sample collection, which is among the fastest responses in the personalized medicine industry.

The clinical utility of GEN has been evaluated in three previous prospective trials. Hall-Flavin et al.(10) reported the results of an open-label pilot study (n = 44) comparing GEN to treatment as usual (TAU) without the benefit of pharmacogenomic testing. The GEN guided arm demonstrated a 30.8% improvement in the 17-item Hamilton Depression Rating Scale (HAM-D₁₇) score by the end of the 8 week treatment period, compared to an 18.2% improvement in the TAU arm (p = 0.04). Results of the larger (n = 165) open-label trial(11) mirrored these findings, demonstrating a 46.9% improvement in HAM-D₁₇

score in the GEN arm, compared to a 29.9% improvement in the TAU arm ($p < 0.0001$). The third trial used a randomized, double-blind trial design ($n = 51$)(12). Due to the small sample size, the trial was underpowered to detect a significant difference in improvement between the two arms (TAU and GEN). However, effect sizes of improvement reflected those seen in previous trials. The GEN group experienced a 30.8% improvement in HAM-D₁₇, compared to 20.7% in TAU. Odds ratios for response were calculated, showing that GEN-guided participants had a 2.14 times greater likelihood of response compared to TAU participants, which was similar to the 4.67 (smaller trial) and 2.06 (larger trial) odds ratios calculated for the other two earlier studies.

The GEN test can also predict those patients with greater healthcare utilizations, disability days, and other events who were prescribed psychotropic medications whose metabolism and brain responses are not optimally matched with the individual's genetic profile(13).

3.3 Enhanced-GeneSight Psychotropic (E-GEN)

The current GEN test lacks predictive genes for a major complication of antipsychotic drug use: antipsychotic-induced weight gain (AIWG).

An enhanced version of the GEN test, E-GEN, was developed by incorporating 6 new genes (represented by 7 SNPs) patented by CAMH and licensed by Assurex that are predictive for AIWG, to those used in the GEN algorithm (Table 1). An increasing risk level associated with AIWG is estimated by an increasing number of risk genotypes that a given patient possesses among the 7 SNPs.

Table 1. Antipsychotic-Induced Weight Gain Markers. MC4R, melanocortin 4 receptor; CNR1, cannabinoid receptor 1; NPY, neuropeptide Y; GCG, glucagon-like peptide 1 gene; HCRTR2, orexin/hypocretin receptor 2; NDUFS1, NADH dehydrogenase (ubiquinone) Fe-S protein 1.

Gene	Polymorphism
MC4R	Rs489693
CNR1	Rs806378
NPY	Rs16147
GCG	Rs13429709
HCRTR2	Rs3134701 Rs4142972
NDUFS1	Rs6435326

3.4 Study Rationale

Previous studies utilizing an open-label design have shown significant improvement in patient outcomes following use of the GEN test(11). However, although effect sizes were

similar to those seen in the open-label studies, a small (n = 51) blinded, randomized controlled trial(12) (RCT) did not detect a statistically significant outcome. Therefore, the first rationale for this trial is to utilize a double-blinded RCT design to replicate previous findings of improvement in clinical outcomes in participants treated with the benefit of GEN testing. Another rationale for this study is to determine the added benefit of using E-GEN testing, as compared to GEN testing, to guide treatment selection based on pharmacogenomic information. Furthermore, this trial also intends to develop an evidence-based case for the value of GEN and E-GEN to Canadian healthcare payers.

It is expected that results from this trial will be used to inform guidelines for the use of pharmacogenomic testing in the treatment of MDD. Results may also be shared with regulatory bodies in Canada and abroad.

3.5 Choice of Comparators

The comparator chosen for this study is treatment as usual (TAU) which provides a “real world” comparison of standard of care with patients who receive GEN or E-GEN test results.

4.0 OBJECTIVES

4.1 Hypothesis

GEN and E-GEN reduces MDD symptoms and is more cost-effective than TAU for patients suffering from MDD and having had – within the current episode – an inadequate response to at least one psychotropic medication included in GEN. Furthermore, E-GEN improves predictions of patients’ clinical responses and provides greater clinical utility as compared to GEN.

4.2 Primary Objectives

The first primary objective of this study is to compare the efficacy of GEN to TAU in improving response to psychotropic treatment in outpatients suffering from a major depressive disorder (MDD) and having had – within the current episode - an inadequate response to at least one psychotropic medication included in GEN.

The second primary objective for this study is to validate the utility of the new CAMH markers and demonstrate the superior predictive capabilities and greater clinical utility of E-GEN as compared to GEN.

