6.2.2 Exclusion Criteria

Any of the following conditions are cause for exclusion from the study:

1. Patients posing a serious suicidal risk and/or in need of immediate hospitalization as judged by the Investigator;
2. Patients with a diagnosis of Bipolar I or II disorder;
3. Patients with a current Axis I diagnosis of:
 - Delirium
 - Dementia
 - Amnestic and/or other cognitive disorder
 - Schizophrenia or other psychotic disorder;
4. Patients having experienced hallucinations, delusions, or any psychotic symptomatology within the current depressive episode or during prior depressive episodes;
5. Patient is currently in an inpatient facility;
6. Patients with a history of hypothyroidism unless taking a stable dose of thyroid medication and asymptomatic or euthyroid for at least 6 months;

7. Patients who meet DSM-IV-TR criteria for any significant current substance use disorder;
8. Patients with:
 - hepatic insufficiency (three times the upper limit of normal (ULN) for aspartate aminotransferase (AST) and/or alanine aminotransferase (ALT)); liver transplant recipient; cirrhosis of the liver;
 - malignancy (except basal cell carcinoma) and/or chemotherapy within 1 year prior to screening; malignancy more than 1 year prior to screening must have been local and without metastasis and/or recurrence, and if treated with chemotherapy, without nervous system complications;
 - significant unstable medical condition or life threatening disease with anticipated survival of less than 6 months;
 - need for therapies that may obscure the results of treatment and/or of the study;
9. Participation in another clinical trial within 30 days of the screening visit;
10. Anticipated inability to attend scheduled study visits;
11. Patients who in the judgment of the Investigator may be unreliable or uncooperative with the evaluation procedure outlined in this protocol;
12. Patients with a history of prior pharmacogenomic testing;
13. Any change in psychotropic medication (including change in dosage) between screening and baseline;
14. Patients currently receiving electroconvulsive therapy (ECT), deep brain stimulation (DBS) or transcranial magnetic stimulation (TMS) treatments, or currently scheduled to receive maintenance treatments of ECT, DBS, or TMS during the course of the study;
15. Patients who self-report to be pregnant or lactating;
16. Patients with a history of gastric bypass surgery

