7.1.2 Enhanced GeneSight Psychotropic (E-GEN)

All procedures for patients randomized to the E-GEN arm will be the same as for patients randomized to the GEN arm except that for E-GEN, the pharmacogenomic laboratory will also analyze each patient's genotypes and corresponding phenotypes for the 7 CAMH markers for AIWG. The treating clinicians will receive an interpretive report that reflects all of the E-GEN genes.

Guided by the results from E-GEN, the treating physician may decide to modify a participant's psychotropic medication, in terms of type of medication, dose, dose regimen and/or number of medications.

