##### **2.1.2.2 Evaluate the following for GEN vs E-GEN:**

- Mean percentage change from baseline in HAM-D17 at Week 8
- Percentage of responders in HAM-D17 at Week 8
- Percentage of remitters in HAM-D17 at Week 8

**The treatment groups used for all subsequent analyses (all scales at each time point) will depend on the results in 2.1.2.2**

- If GEN is not statistically different than E-GEN at any endpoint, GEN and E-GEN treatment arms will be combined and compared to TAU
- If E-GEN is statistically superior to GEN at any endpoint, E-GEN will be compared to TAU
- If GEN is statistically superior to E-GEN at any endpoint, GEN will be compared to TAU

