### **2.1.4 Exploratory, Safety, and Tolerability Objectives**

- Mean percentage change in Generalized Anxiety Disorder 7-item (GAD-7) scale from baseline to end of Week 8, Week 12, Month 6, Month 9, Month 12;
- Percentage of responders and remitters at Week 8, Week 12, Month 6, Month 9, Month 12 on GAD-7 (see definition in 7.1 and 7.2);
- Change in SF-36 from baseline to end of Week 12, Month 6, Month 9, and Month 12;
- Percentage of responders at Week 12, Month 6, and Month 12 on SF-36 (see definition in 7.1);
- Mean percentage change in the Clinical Global Impression: Severity of Illness (CGI-S) from baseline to end of Week 12 and Month 12;
- Percentage of responders and remitters at Week 12 and Month 12 on CGI-S in each treatment group (see definition in 7.1 and 7.2);

- Percentage responders at Week 12 and Month 12 on CGI-I (Clinical Global Impression: Global Improvement) in each treatment group (see definition in 7.1);
- Percentage responders at Week 12 and Month 12 on CGI-IE (Clinical Global Impression: Efficacy Index) in each treatment group (see definition in 7.1);
- Compare congruence of medications between treatment groups at Week 8, Week 12, Month 6, Month 9, and Month 12 (see 7.5 for definition);
- Percentage of subjects who experienced adverse events (AE) at Week 8, Week 12, and Month 12;
- Change in Udvalg for Kliniske Undersogeler (UKU) side effect rating scale; Frequency, Intensity and Burden of Side Effects Ratings (FIBSER); and weight gain from baseline to Week 8, Week 12, and Month 12;
- Percentage of patients compliant with medications at Week 8, Week 12, Month 6, Month 9, and Month 12 between treatment groups using Brief Adherence Rating Scale (BARS) and prescription filling data

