### **5.3 Safety and Tolerability Analysis**

Descriptive statistics for the number of AE's by treatment and week will be generated. The percentage of subjects who experienced AE's may be analyzed using a Generalized Linear Mixed model. The model would include treatment, gender, age, and baseline HAM-D17 score. Continuous measures including UKU, FIBSER, and weight gain may be analyzed in a similar manner as for the primary efficacy variable above.

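### E-GEN adds only weight-gain markers to GEN, yet the SAP compares the two inferentially only on Week 8 HAM-D17 endpoints and pre-specifies no E-GEN vs GEN contrast on weight

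*Protocol*

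**What the plan says.** **What E-GEN is.** Protocol 3.3 describes E-GEN as made by "incorporating 6 new genes (represented by 7 SNPs) patented by CAMH and licensed by Assurex that are predictive for AIWG". Protocol 7.1.2 keeps all procedures as in the GEN arm, apart from also determining "genotypes and corresponding phenotypes for the 7 CAMH markers for AIWG".

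**What is to be shown.** Protocol 4.2 makes it a primary objective to validate the new markers and "demonstrate the superior predictive capabilities and greater clinical utility of E-GEN as compared to GEN". Protocol 4.3 adds a three-arm secondary comparison of side effects that includes weight gain. Protocol 8.2.1 (xi) names weight and waist-to-hip ratio as the measures of this side effect.

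**What is tested.** Protocol 16.1.3 writes the hypotheses for both primary objectives in terms of HAM-D17 percentage improvement. SAP 1.2 states that the SAP supersedes the protocol's analysis plan. SAP 2.1.1 has one primary objective, GEN vs TAU. SAP 2.1.2.2 places GEN vs E-GEN among the secondary objectives, with three endpoints: "Mean percentage change from baseline in HAM-D17 at Week 8", responders and remitters. It then sets the groups for every later analysis to one of three pairs: GEN and E-GEN combined vs TAU, E-GEN vs TAU, or GEN vs TAU.

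**Where weight stands in the SAP.** Section 2.1.4 lists change in side-effect scales "and weight gain from baseline to Week 8, Week 12, and Month 12". Section 5.3 says: "Continuous measures including UKU, FIBSER, and weight gain may be analyzed in a similar manner as for the primary efficacy variable above". Weight is absent from the variable list in 2.2.3, and the SAP does not mention waist-to-hip ratio.

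**The concern.** The contrast meant to judge E-GEN uses an outcome that its added markers do not target. HAM-D17 does not score weight gain; item 16 (Protocol Appendix II) scores weight loss only. The natural outcome is measured but has no planned comparison between the two tests.

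Two things are at stake. A null HAM-D17 result could be read as showing that E-GEN adds nothing, and the arms would then be merged. An effect of E-GEN on weight, if there is one, would be diluted by the merging, and any E-GEN vs GEN estimate would have to come from an unplanned analysis. That is weak support for something the protocol calls a primary objective.

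**Working it through.** **1. Is there a planned E-GEN vs GEN contrast on weight?**
- Protocol 16.1.3: hypotheses on HAM-D17 only.
- Protocol 16.1.5: relates a green/yellow/red composite to outcomes such as HAM-D17 improvement; the weight-risk genotypes are not related to weight.
- SAP 2.1.2.2: GEN vs E-GEN on HAM-D17 endpoints only; none of the three branches that follow contains E-GEN vs GEN.
- SAP 2.1.4 and 5.3: weight listed, modelling optional, no pair of arms named.
- SAP 4: a column per arm and, where suitable, effect estimates with confidence intervals; no pair of arms named.

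No such contrast is pre-specified.

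**2. The plan's own figure.** Protocol 10.0 gives 190 per arm for a HAM-D17 effect of 0.30 at 90% power, alpha 0.05 and 16.7% discontinuation by Week 8. The usual two-sided formula gives 2 × (1.960 + 1.282)² / 0.30² = 234 per arm, and 234 / 0.833 = 281 with discontinuation. So 190 is not reproduced this way. How the intraclass coefficient of 20% entered the calculation is not stated. This is a separate matter. Below, 190 is taken as the number enrolled, so the evaluable number at Week 8 is 190 × 0.833 = 158 per arm.

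**3. How often would the arms be pooled if E-GEN does not affect HAM-D17?** The rule is read as pooling when none of the three endpoints differs at 0.05.
- Independent endpoints: 0.95³ = 0.857.
- Fully correlated endpoints: 0.95.
- Simulation with 158 per arm (assumed baseline mean 20, SD 4; mean fall 25%, SD 32%): at least one difference in 11.4% of runs, so pooling in 88.6%.

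**4. What pooling does to a weight effect.** Let mean weight change be g in GEN, g − D in E-GEN and t in TAU. With equal arms the pooled mean is g − D/2, and its difference from TAU is (g − t) − D/2. If g = t, a saving of D appears as D/2.

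**5. What the HAM-D17 contrast can say about the markers.** Entry does not require an antipsychotic (Protocol 6.2.1). The exclusions cover bipolar disorder and "Patients having experienced hallucinations, delusions, or any psychotic symptomatology within the current depressive episode or during prior depressive episodes". The share of antipsychotic users is not given. As an illustration, assume a HAM-D17 effect of 0.30 SD confined to users, so that the whole-arm effect is 0.30 × share. Power is about Φ(effect × √(158/2) − 1.96):
- share 20%: effect 0.06, power about 8%
- share 30%: effect 0.09, power about 12%
- share 50%: effect 0.15, power about 27%
- all patients: effect 0.30, power 76%

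**6. What a weight contrast could detect at Week 8.** The documents give no SD for weight, so results are in SD units. Detectable difference at 80% power, two-sided 0.05: 2.80 × √(2/n).
- All patients, n = 158 per arm: 0.32 SD
- Users at an assumed 30%, n = 47: 0.58 SD
- Users at an assumed 20%, n = 32: 0.70 SD
- Users at an assumed 10%, n = 16: 1.0 SD

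**The case against.** **Weight is not ignored.** It is a three-arm secondary objective in Protocol 4.3, it is in SAP 2.1.4 at three time points, and SAP 4 foresees tables by arm with effect estimates. This stands. A reader might infer that E-GEN is never compared with GEN on weight, or that the objective cannot be answered. The documents do not support either: the data exist by arm and a descriptive comparison is possible. What is missing is a named, mandatory contrast.

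**The reach of the grouping rule is unclear.** SAP 2.1.2.2 applies it to every later analysis, but its gloss speaks of scales, and weight is not a scale. Sections 2.1.2.3 and 2.1.3 repeat the rule and 2.1.4 does not. SAP 5.2 compares congruence between GEN and TAU whatever the rule gives. So it is not certain that weight would be pooled. Even if it is not, 2.1.4 names no E-GEN vs GEN contrast.

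**HAM-D17 is a legitimate outcome for E-GEN.** Protocol 4.1 expects better prediction of clinical response, and 7.1.2 lets the report change drug, dose or number of drugs. This stands: HAM-D17 covers part of clinical utility, and nothing in the documents supports dismissing a positive result as chance. It remains a weak test of what the markers add.

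**Current antipsychotic users are not the only patients who could benefit.** Appendix I lists 14 antipsychotics and Protocol 7.2 allows treatment changes at any time, so the report could influence whether one is started. This stands, and it is why the all-patient contrast should lead.

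**The SAP has already made E-GEN secondary.** True, but the protocol still calls it primary. That mismatch needs resolving and does not supply the missing contrast.

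**Conclusion.** The point holds in this form: the protocol's E-GEN objective has no pre-specified test on the outcome that E-GEN's added markers target, and the SAP grouping rule offers no branch that would supply one. A null HAM-D17 comparison followed by pooling would say little about the markers.

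The pooling range of 86% to 95% assumes no E-GEN effect on HAM-D17 and three tests at 0.05. The gap itself does not depend on that range, because no branch contains the contrast. The halving of a weight effect assumes that the rule covers weight and that GEN and TAU have equal weight change. The 0.32 SD applies at Week 8 only, since the 16.7% is discontinuation by that visit; later visits will have fewer patients. All figures for antipsychotic users rest on assumed shares.

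**What to change.** 1. In the SAP, pre-specify change in weight from baseline, E-GEN vs GEN, in all randomised patients, adjusted for baseline weight. Name one principal time point from those already scheduled and treat the others as supportive. The population must be stated, because the SAP otherwise gives precedence to the per-protocol set.
2. State that weight and waist-to-hip ratio are analysed by the three randomised arms and are exempt from the grouping rule in 2.1.2.2.
3. Make the weight analysis in 5.3 mandatory, and add weight to 2.2.3.
4. Report the same contrast in patients on an Appendix I antipsychotic at screening, as exploratory, with its confidence interval. Screening status is recorded before any report is released, so the report cannot affect it, but it misses patients started on an antipsychotic later.
5. Keep GEN vs E-GEN on HAM-D17, and state that a null result is not evidence that E-GEN lacks utility.
6. Reconcile the status of the E-GEN objective, primary in the protocol and secondary in the SAP. An arm contrast on weight addresses utility. If the claim about prediction stays, the SAP should say which analysis serves it.

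**Cost.** SAP wording and a small number of models on data already scheduled: weight is taken at baseline, Weeks 4, 8 and 12, and Month 12. The main drawback is the imprecise subgroup estimate.
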